joint mobility [6][10][11]. Coupled with appropriate physical therapy, it can also strengthen muscles, increase joint stability, avoid joint contracture, and reduce the possibility of re-bleeding [2][4][7][8]. Past literature has recommended that exercise therapy should be provided to patients with hemophilia. However, there is currently no consensus on the type, severity, and frequency of safe exercise programs, especially for hemophilia patients with polyarthropathy [12][13]. In addition, manual therapy is another effective physical therapy intervention to increase biomechanical extensibility and joint function by mobilizing and stretching joints and soft tissues (including muscles and nerves). Although the use of manual therapy for patients with hemophilia is increasing, most studies focus on exploring the mobility of single joint [12][13], and the number of studies on manual therapy for multiple joints in the past literature is limited. As hemophilia patients' life expectancy increases, workforce participation, overall functioning, and independent activity daily living have become current issues and challenges. Therefore, much more evidence-based research is needed on manual therapy and exercise programs in hemophilia patients with polyarthropathy. Therefore, this study intends to investigate the impact and effectiveness of individualized physical therapy based on case conditions (severe hemophilia with polyarthropathy) [3]. It is hoped to try to combine different physical therapy techniques (manual therapy and exercise intervention) to improve pain, muscle strength, joint health, cardiopulmonary endurance, and thereby enhance the overall quality of life [5][7][8][9].

V. Purpose

Whether the use of individualized physical therapy combined with manual therapy and exercise intervention effectively improve joint status, muscle strength, pain, cardiopulmonary endurance, etc. for severe hemophilia patients with polyarthropathy, and at the same time prevent the possibility of recurrence of bleeding.

VI. Methods

A. Selection criteria and number of people.

1. Number of subjects: It is expected that 10 subjects.

2. Inclusion criteria:

- a. Over 20 years old and diagnosed with severe hemophilia
- b. Those who receive prophylaxis regularly
- c. There are more than 2 target joints (arthrosis)

3. Exclusion criteria:

- a. Unable to sign the informed consent form
- b. Any neurological disease or major musculoskeletal system disease (such

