This study employed the non-parametric statistical software SPSS version 20.0, with a significance level set at $p < 0.05$. Descriptive statistics were used to describe the characteristics and distribution of the basic data variables. Furthermore, the Wilcoxon signed-rank test was utilized to examine differences in joint condition, muscle strength, pain, and cardiopulmonary endurance before intervention, and at 6 and 12 weeks post-intervention. The statistical analysis included comparisons between pre-test and mid-test, as well as pre-test and post-test, to mitigate the risk of incomplete data due to participants dropping out before completing the final test. Additionally, sample size calculations were performed using G*Power. The effect size was based on the visual analogue scale measuring perceived pain in patients with hemophilic knee joint disease, set at $d = -1.30$ [20]. With an alpha level of 0.05 and a power value of 0.95, the required sample size was determined to be 9 participants. To account for potential sample attrition, a 10% increase in sample size was applied, resulting in a projected total sample size of 10 hemophilia patients [12].

4. Questionnaires or other research-related scales:

This study utilized the following scales and questionnaires to assess changes in joint condition, pain, cardiopulmonary endurance, functional level, and quality of life in patients before intervention, and at 6 and 12 weeks post-intervention, in order to confirm treatment efficacy:

a. **Hemophilia Joint Health Score (HJHS):** This scale is designed to monitor joint

changes over time in hemophilia patients. It evaluates the swelling of the elbow, knee, and ankle joints, duration of persistent swelling, muscle atrophy, presence of crepitus during movement, reduction in range of motion, joint pain level, muscle strength, and overall gait performance. **Validity:** The scale has high evidence of both convergent validity and discriminant construct validity for detecting joint damage in adults with hemophilia, making it suitable for this population. **Reliability:** The scale demonstrates excellent reliability, with test-retest (ICC=0.89) and inter-observer (ICC=0.83) values.[14] The scale was assessed and completed by physical therapists.

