- b. **Visual Analog Scale (VAS):** This scale evaluates pain in target joints of hemophilia patients, converting the results into scores to provide a clearer understanding of overall pain experience. **Reliability:** The scale exhibits high reliability with an ICC of 0.97 (95% CI 0.96 to 0.98). Research indicates that it is a reliable and valid instrument. [15]
- c. **6-Minute Walk Test (6MWT):** This test assesses the overall cardiopulmonary endurance of patients. **Reliability:** The reliability is good, with test-retest values ranging from 0.88 to 0.94. **Validity:** It has moderate convergent validity, with a correlation of 0.71 to 0.82 with treadmill performance. [16] The assessment and completion of this scale are performed by physical therapists.
- d. **Hemophilia Activity List (HAL):** This scale evaluates functional activities in hemophilia patients across seven domains: lower limb function, upper limb function, transportation, self-care, household tasks, leisure activities and exercise, and modification or use of assistive devices. **Validity:** The HAL demonstrates good construct and convergent validity. **Reliability:** It shows good internal consistency, with a Cronbach's alpha ranging from 0.61 to 0.96. [17] This scale is completed by the patients themselves.
- e. **EQ-5D-5L:** This scale assesses patients' quality of life, including mobility, self-care, usual activities, pain or discomfort, and anxiety or depression. **Validity:** It exhibits satisfactory construct validity for measuring quality of life in hemophilia patients. Research indicates that this scale has both good reliability and validity. [18] [19] The scale is completed by the patients themselves.
- f. **Patient Diary Card:** This card assesses patient status, including basic information and daily living activities, and records the content of each treatment session. The documentation is completed by physical therapists.

VII. Handling of Research Materials:

- A. Collection and processing of paper, electronic data / samples during the study:
The principal investigator is responsible for explaining the experimental procedures and distributing consent forms. The principal investigator also oversees the execution of exercise and manual therapy, while the co-investigator handles clinical

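### VI.B.3 names no primary outcome, deciding time point or sidedness for its unadjusted Wilcoxon tests; if any one significant result were read as improvement, three instruments at two times would give about a 9–13% chance of a false one, against 2.0–2.4% for a single test.

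*Combined protocol and SAP*

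**What the plan says.** All references are to the combined protocol and SAP. VI.B.3 sets significance at p < 0.05 and says that "the Wilcoxon signed-rank test was utilized to examine differences in joint condition, muscle strength, pain, and cardiopulmonary endurance before intervention", with follow-up measurements in weeks 6 and 12. It adds: "The statistical analysis included comparisons between pre-test and mid-test, as well as pre-test and post-test". The reason given for using both comparisons is "to mitigate the risk of incomplete data due to participants dropping out before completing the final test". The section does not say which outcome is primary, which comparison decides, whether the tests are one- or two-sided, or whether any adjustment is made for several tests.

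The same section sizes the trial on pain: "The effect size was based on the visual analogue scale measuring perceived pain in patients with hemophilic knee joint disease". With d = −1.30, alpha 0.05 and power 0.95 it arrives at 9 subjects, raised by 10% to 10.

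VI.B.4 introduces the scales as used "in order to confirm treatment efficacy". Under VI.B.4.a the HJHS items include "reduction in range of motion, joint pain level, muscle strength, and overall gait performance", and no other listed instrument measures muscle strength. VI.B.4.b says of the VAS: "This scale evaluates pain in target joints of hemophilia patients, converting the results into scores", with the aim of showing the patient's pain as a whole. VI.A.2 requires more than two target joints per subject. No rule says how the joints are combined.

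**The concern.** The 0.05 in the sample-size calculation describes one VAS comparison. The analysis section plans several comparisons at that same level and does not say which of them carries the conclusion. Sections V and IX.A list pain, joints, muscle strength and endurance side by side without ranking them.

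Three choices are left open until the results are known:

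- the outcome;
- the time point, because week 6 is justified as a guard against dropout but no rule says when it decides;
- the way several joints become one pain score.

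In a study of 10 subjects without a control group, a deciding test fixed in advance is one of the few protections available. Without it, a reader cannot tell a planned result from the most favourable of several.

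**Working it through.** **1. The plan's own figure.** Power is taken from the noncentral t distribution with effective size n × ARE (the asymptotic relative efficiency of the Wilcoxon test) and noncentrality d√(n × ARE).

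- One-sided, normal changes (ARE = 3/π = 0.955): n = 9 gives effective size 8.59, noncentrality 1.30 × √8.59 = 3.81 and power 0.964. The plan's 9 is reproduced.
- Two-sided, normal changes: 11 subjects are needed (power 0.964).
- Two-sided, logistic changes (ARE = π²/9 = 1.097): 9 subjects (power 0.951).
- Dropout: 9 × 1.1 = 9.9, rounded up to 10.

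The stated n therefore does not reveal the sidedness.

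**2. One test.** With no true change and no ties, all 2ⁿ sign patterns are equally likely. For a two-sided test at 0.05 the critical rank sum is 5 at n = 9 and 8 at n = 10. The chance of a false result in the direction of improvement is 10/512 = 1.95% and 25/1024 = 2.44%.

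**3. Number of tests.** Three instruments cover the tested domains: HJHS, VAS and 6MWT. Three × two comparisons = 6 tests. If muscle strength were a separate outcome, four × two = 8.

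**4. Bounds that need no simulation.**

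- Six tests, any correlation: at most 6 × 1.95% = 11.7% (n = 9) or 6 × 2.44% = 14.6% (n = 10).
- Week 12 only, three independent outcomes: 1 − (1 − 0.01953)³ = 5.75% (n = 9) and 1 − (1 − 0.02441)³ = 7.15% (n = 10).

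**5. Simulation.** Correlated normal changes with no true effect, exact critical values, 100,000 trials per setting. Correlations are assumed: 0 or 0.5 between outcomes, 0.5 or 0.7 between times. Chance of at least one false improvement, two-sided:

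| Setting | Week 12 only | Both times |
|---|---|---|
| n = 9, three outcomes | 5.1–5.7% | 8.7–10.5% |
| n = 10, three outcomes | 6.3–7.2% | 10.7–13.1% |
| n = 9, four outcomes | 6.4–7.7% | 11.0–13.9% |
| n = 10, four outcomes | 8.0–9.5% | 13.3–16.9% |

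In the last row, both times, a correlation of 0.5 between outcomes gives 13.3–14.1%. Only zero correlation gives 15.8–16.9%.

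If the tests are one-sided, three outcomes give 16.6–24.4% over both times and 10.4–14.2% at week 12, against 4.2–4.9% for one test.

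**6. Sensitivity, six to eight tests, two-sided.**

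- Wider correlations (0–0.7 between outcomes, 0.3–0.8 between times): 7–17% over both times, 5–9% at week 12.
- Ties and zeros (changes rounded to half an SD): 7–11% with exact p-values (one test 1.4–1.6%), 10–17% with the normal approximation (one test 2.3–2.4%).

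**7. Joint score.** Assume three joints with between-joint correlation 0.3–0.7. Choosing afterwards between the mean and the worst baseline joint raises one two-sided week-12 VAS test from 2.0–2.4% to 2.9–4.1%.

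**8. Exact or approximate p-values.** Without ties, the two give the same two-sided critical values at n = 9 and 10. They differ at n = 8 two-sided (true error 5.5% approximate, 3.9% exact) and at n = 10 one-sided (5.3% against 4.2%).

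**The case against.** **The plan never says that one significant result proves efficacy.** This stands. The VI.B.4 phrase about confirming efficacy introduces a list of scales and is not a success criterion. A reader might infer that the plan has an error rate of 9–17%. The documents do not support that: the percentages apply only if any single significant result is read as improvement.

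**The top of the range fits the documents poorly.** This also stands. Reaching 17% needs muscle strength as a separate outcome uncorrelated with the others. No such instrument is listed, and the HJHS contains both strength and pain items, so some correlation is likely.

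**The count could be higher.** VI.B.4 also covers function and quality of life, and testing the HAL and EQ-5D-5L as well would give about 15–24%. But VI.B.3 names no test for them, so that figure is not supported.

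**VAS pain is obviously primary.** It is the natural candidate because it sized the trial, but nothing designates it.

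**Week 6 is only a fallback.** That is a fair reading of the stated reason and lowers the figure to 5–7%. It does not supply the missing rule.

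**The VAS is meant to give one overall score.** The intention is there and only the formula is missing. The effect of that gap alone is small (step 7).

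**The sample size shows that the tests are one-sided.** A reader might infer this from n = 9, but a two-sided calculation with a logistic distribution gives 9 as well.

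**Conclusion.** The point holds as an omission with a measurable consequence and should be fixed. With the three listed instruments, 9–10 subjects, the assumed correlations and no ties, reading any one significant result as improvement carries a two-sided false-improvement chance of about 9–13%, or 5–7% if only week 12 counts, against 2.0–2.4% for one test. It reaches at most about 17% (9% at week 12) only if muscle strength is a separate, uncorrelated outcome. Confidence is medium, because the correlations are assumed and the plan's decision rule is unknown.

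The model also assumes no change without an effect. In an uncontrolled before-after study, time trends and regression to the mean can move all outcomes together. Fixing the deciding test controls the multiplicity but does not make the change attributable to the intervention.

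**What to change.** In VI.B.3:

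1. Name VAS pain as the single primary outcome, with one score per subject fixed in advance, for example the mean over the target joints identified at baseline.
2. Make baseline against week 12 the deciding comparison and fix how dropouts enter it. One option is to use the week-6 score where week 12 is missing, which keeps the plan's own safeguard, with completers only as a sensitivity analysis. VIII.A withdraws subjects after repeated discomfort, so dropout may be related to outcome and a completers-only primary analysis could favour improvement. Also say how a subject with neither score is handled.
3. State the sidedness and specify exact Wilcoxon p-values.
4. Report week-6 VAS and all other scales as secondary, with median change and 95% CI and no confirmatory claim. State whether muscle strength is a separate measure or an HJHS item.
5. Limit the conclusion to within-subject change over 12 weeks, because there is no comparator and subjects also receive traditional physical therapy (VI.B.1.e).

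The change needs a few sentences and no new data or subjects. It has these costs:

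- A nominal p < 0.05 on a secondary scale or at week 6 no longer counts as confirmation.
- A mean over joints can dilute a change in one joint.
- Week-6 scores can understate or overstate the week-12 change.
- Stating the sidedness exposes the power. At d = 1.30 with normal changes, 10, 9 and 8 analysed subjects give 0.94, 0.89 and 0.83 two-sided, or 0.97, 0.96 and 0.92 one-sided, against the planned 0.95.

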- e. Intervention schedule: Once a week for three months (about 12 weeks), 30 minutes of traditional physical therapy plus 30 minutes of individualized physical therapy intervention, about 1 hour.
- f. Questionnaires and scales were conducted before intervention, at the 6th week after intervention (mid-term intervention) and at the 12th week (end of intervention) to evaluate changes in joint status, pain, cardiopulmonary endurance, functional level, and quality of life.
- g. The patient daily note includes exercise duration and content, intensity, manual

therapy techniques, bleeding, and remark on special situations.

(i) Exercise duration and content, intensity, and manual therapy techniques:

Gradually increase according to the current situation and ability, as mentioned above.

(ii) Bleeding: It can be determined by the range of motion of the joint, the severity of the pain, and the appearance of redness, swelling and heat.

(iii) Notes on special circumstances: If there are any special things in this study, please note them down.

h. Subjects will be given NT\$500 each in the 6th and 12th weeks respectively, for a total of NT\$1,000 in traffic allowance.

2. Subject follow-up or necessary rehabilitation plan:

During the study period, subjects will come to the treatment room for individualized physical therapy once a week, and safety status will be tracked regularly.

After the study is completed, if necessary (depending on subject's opinion and therapist's judgment), rehabilitation plan will be arranged based on the actual situation.

3. Treatment effect evaluation and statistical analysis methods:

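### Function and quality of life are measured but have no planned analysis, no primary outcome or time point is named, and the single-arm design cannot show that bleeding is prevented

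*Combined protocol and SAP*

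**What the plan says.** Section VI.B.3 applies the Wilcoxon signed-rank test to "examine differences in joint condition, muscle strength, pain, and cardiopulmonary endurance before intervention" and at weeks 6 and 12. Each outcome gets two comparisons, baseline to week 6 and baseline to week 12, at the 5% level. The only other analysis is descriptive: "Descriptive statistics were used to describe the characteristics and distribution of the basic data variables".

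The measurement sections carry a different list. VI.B.4 says the scales serve "to assess changes in joint condition, pain, cardiopulmonary endurance, functional level, and quality of life in patients before intervention" and at weeks 6 and 12, as confirmation of efficacy. VI.B.1.f agrees: "to evaluate changes in joint status, pain, cardiopulmonary endurance, functional level, and quality of life". Function is measured by the HAL ("This scale evaluates functional activities in hemophilia patients across seven domains") and quality of life by the EQ-5D-5L, described through five dimensions. No overall score is specified for either. Quality of life is in the title, and IX.A presents it as the final benefit.

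No outcome or time point is called primary. For the sample size, "The effect size was based on the visual analogue scale measuring perceived pain in patients with hemophilic knee joint disease". VI.B.4.b says of the VAS: "This scale evaluates pain in target joints of hemophilia patients". The same sentence adds that ratings become scores giving a picture of pain overall. VI.A.2 requires more than two target joints per subject.

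Section V includes preventing recurrent bleeding among the aims. Bleeds go in the daily note (VI.B.1.g). The design is one group of 10, with no control arm, no pre-study bleeding period and no planned bleeding summary.

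**The concern.** Followed to the letter, the plan yields no result for function or for quality of life, a title outcome. If the two scales are analysed anyway, seven HAL domains and five EQ-5D-5L dimensions leave room to choose the score after the data are seen.

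With no primary outcome and no main time point, nothing says which of the comparisons answers the trial's question, and chance findings accumulate across them. Even the outcome that drives the sample size is not yet a single variable, because several joints are rated per subject and the combining rule is missing.

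On bleeding, 12 weeks of observation in one group can say how many bleeds occurred. It cannot say how many would have occurred without the intervention.

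**Working it through.** **1. The lists side by side.**

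| Domain | Measured (VI.B.1.f, VI.B.4) | Tested (VI.B.3) |
|---|---|---|
| Joint condition | yes (HJHS) | yes |
| Pain | yes (VAS) | yes |
| Cardiopulmonary endurance | yes (6MWT) | yes |
| Function | yes (HAL) | no |
| Quality of life | yes (EQ-5D-5L) | no |
| Muscle strength | only as a part of the HJHS | yes |

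Two of the five named scales have no planned comparison or summary.

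**2. The plan's own figure.** With |d| = 1.30, alpha 0.05 and power 0.95, a one-sided signed-rank calculation (n scaled by 3/π) gives 9 subjects, with power 0.964. Two-sided, the same method needs 11, with power 0.910 at 9 and 0.943 at 10. Sidedness is not stated. For attrition, 9 × 1.1 = 9.9, rounded up to 10. So 9 reproduces, and this point does not depend on it. Since the plan expects attrition from 10 to 9, both sizes are used below.

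**3. Multiple tests.** The minimum count is 4 domains × 2 comparisons = 8. It is a minimum because VI.B.3 fixes no score for any domain. The exact two-sided signed-rank test at nominal 5% has true size 0.0488 (n = 10) or 0.0391 (n = 9). If the tests were independent:
- n = 10: 1 − (1 − 0.0488)^8 = 33%
- n = 9: 1 − (1 − 0.0391)^8 = 27%

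The tests are not independent. In simulation under no effect (100,000 runs, shared baseline, independent equal-variance visits, between-domain correlation 0.5 to 0), the chance of at least one false positive is:
- n = 10: about 28–32%
- n = 9: about 23–26%

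If strength is taken from the HJHS and correlates 0.8 with it, the others at 0.5, the figures fall to 26% and 22%.

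**4. Open VAS rule.** Assumptions: 3 joints (the fewest the entry criterion allows), between-joint correlation 0.7 to 0.3, half of the variance stable between visits, no true effect. False-positive rate for week-12 pain:

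| Rule | n = 10 | n = 9 |
|---|---|---|
| One fixed in advance | 4.9% | 3.9% |
| Mean or worst joint, chosen afterwards | about 7–8% | about 6% |
| Mean, worst or one index joint, chosen afterwards | about 9–11% | about 7–9% |

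**5. Bleeding.** The exact (Clopper-Pearson) upper limit for 0 of 10 subjects with a bleed is 1 − 0.025^(1/10) = 30.8%. For 3 of 10 the interval is 6.7–65.2%. Either describes this group; neither is a comparison.

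**The case against.** The best defence is that this is loose drafting in a small exploratory study. Much of that stands, and it rules out several stronger readings.

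- A reader might infer that the investigators decided not to analyse function and quality of life. The text does not support that. VI.B.4 collects both to show efficacy, so the likely intent was to test them the same way. The omission remains until it is written in.
- A reader might infer that no overall pain score is intended. VI.B.4.b shows that one is; only the formula is missing.
- A reader might infer that any lone significant result will be presented as the finding. VI.B.3 commits to both comparisons for every listed domain, and VAS pain is the only outcome that powers the study. The gap is that pain is not named as primary and no main time point is chosen.
- A reader might take 1 − 0.95^8 = 34% as the error rate. That uses the nominal level and assumes independence; the exact test and correlated outcomes give less.
- A reader might infer that bleeding is not recorded, or that the trial expects to claim prevention. Bleeding is recorded, other sections treat it as safety monitoring, and IX.A lists no bleeding benefit. The mismatch lies in the wording of section V.
- A reader might see a conflict between exercise on 3–5 days a week (VI.B.1.d) and weekly sessions (VI.B.1.e). An exercise prescription and clinic attendance can coexist, and this point does not rely on it.

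Scoring rules may also be in the cited validation papers, which were not available here. VI.B.3 does not adopt any. Nor does a study of this kind need a multiplicity adjustment, and none is asked for.

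**Conclusion.** The point holds and is worth fixing before analysis. Three parts rest on the text alone: HAL and EQ-5D-5L have no planned analysis, no primary outcome or time point is named, and one group without a comparator or a pre-study bleeding period can describe bleeding but cannot show that it was prevented.

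The sizes are illustrative. The error figures assume two-sided exact tests, one score per domain and the stated correlations. The VAS figures also assume three joints and the stated variance split. The documents give none of these correlations or variances. The ranges are about 28–32% (n = 10) or 23–26% (n = 9) for at least one false positive among 8 tests, and about 9–11% or 7–9% for pain if the rule is left open among three choices. The sample-size arithmetic is not in question.

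**What to change.** 1. Add HAL and EQ-5D-5L to the Wilcoxon comparisons in VI.B.3 as secondary outcomes. Write in one summary score for each before the data are seen. The choice of score is the investigators'.
2. Name VAS pain, baseline to week 12, as the single primary outcome. Fix one score over the target joints identified at baseline, with the same joints at every visit: for example the mean, with per-joint values listed descriptively. Label every other comparison secondary.
3. If muscle strength is the HJHS item, report it as a component of the HJHS and not as separate evidence.
4. Restate the bleeding aim as describing bleeding. Report the number of bleeds and the number of subjects with a bleed over 12 weeks, the latter with an exact 95% confidence interval.

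Cost: wording, plus two scales already collected run through a test already planned. No visits or subjects are added. The downsides are:
- The minimum number of tests rises to 6 × 2 = 12, and the simulated chance of at least one false positive to about 36–43% (n = 10) or 31–37% (n = 9). This is why a single primary outcome is needed.
- The planning effect size comes from knee pain, so the stated power carries over to a multi-joint score only if the effect is similar. A mean can also hide change in one joint.
- The bleeding summary will be imprecise, and prevention is no longer claimed.

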assessments and data statistics and analysis. All data is collected and processed by the research team. Paper records are securely locked in the principal investigator's personal filing cabinet, and electronic data is temporarily consolidated and stored on a personal computer.

B. Post-study processing, storage, and retention of paper and electronic data / samples:
To ensure the appropriate handling and security of the data, the research team will utilize a lockable filing cabinet to store paper records securely. Electronic data, once consolidated, will be saved on a personal computer. Upon completion of the study, all research data will be retained for five years. After this period, the principal investigator will be responsible for the destruction of electronic data to ensure privacy. Additionally, paper records containing personal information will be destroyed by incineration through a process managed by Far Eastern Memorial Hospital, to mitigate the risk of data leakage.

VIII. Protection of subjects' rights

A. Potential physical, psychological, and social harm and mitigation measures:
Although the likelihood is low, this study may still cause physical discomfort such as muscle soreness or joint bleeding due to the testing procedures. Therefore, prior to testing, participants will be asked if they regularly receive prophylaxis. If any discomfort occurs during the testing, the procedure will be immediately halted, and appropriate management will be taken. Should the discomfort occur three times, the subject will be withdrawn from the study ahead of schedule. During the testing period, professionals will assist in enhancing the safety of the subjects.

B. Conditions and mechanisms for study suspension / termination or early withdrawal:
Since rehabilitation outcomes may vary among individuals, the therapist will continuously monitor the subject's condition throughout the intervention period. Additionally, subjects may withdraw their consent to participate in the study at any time, and this decision will not affect the therapist's future medical care of the subject. Subjects need not worry about the impact of withdrawal on subsequent rehabilitation treatment (this will be explicitly stated in the consent form), thereby minimizing any psychological pressure or burden.

C. Subject compensation:
Subjects will receive transportation expenses of 500 TWD each at the 6th and 12th weeks, totaling 1000 TWD.

IX. Outcomes

A. Expected results and major benefits:

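### The prophylaxis question asked before testing (VIII.A) repeats an inclusion criterion, does not show whether the current dose was taken, and has no stated action for a 'no' after enrolment

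*Combined protocol and SAP*

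**What the plan says.** Section VIII.A (potential harm and mitigation) accepts that testing may cause muscle soreness or joint bleeding. It presents the mitigation as following from that risk: "prior to testing, participants will be asked if they regularly receive prophylaxis". If discomfort then occurs, the procedure is halted and managed. A further rule reads: "Should the discomfort occur three times, the subject will be withdrawn from the study ahead of schedule".

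Regular prophylaxis is also a condition of entry. Inclusion criterion b in VI.A.2 reads "Those who receive prophylaxis regularly".

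Two records are described. The daily note in VI.B.1.g covers exercise, intensity and manual therapy, and its list ends with "therapy techniques, bleeding, and remark on special situations". Item (ii) of that section says bleeding is judged from range of motion, pain severity, redness, swelling and heat. The Patient Diary Card in VI.B.4.f is described thus: "This card assesses patient status, including basic information and daily living activities, and records the content of each treatment session". Neither description mentions prophylaxis.

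Section VI.B.2 adds that at the weekly visits "safety status will be tracked regularly", without saying what is tracked. Section V makes it part of the study's purpose to "prevent the possibility of recurrence of bleeding".

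**The concern.** The question in VIII.A is the protocol's own answer to a bleeding risk that it names itself. What bears on that risk on a given day is whether the subject has taken the dose due under his own schedule. The question asks about habit, which was settled at entry.

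The stake is patient safety. Subjects have severe hemophilia with several target joints. They receive joint mobilization, passive stretching and resistance that rises over time (VI.B.1.d), and they undergo the Hemophilia Joint Health Score (HJHS) examination and the 6-minute walk test (6MWT) (VI.B.4). A therapist who follows the text exactly could carry out any of these without knowing whether the scheduled dose was taken. The estimation and testing of efficacy are not at stake.

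**Working it through.** No arithmetic applies and the plan gives no figure on this point, so the check sets the relevant sections side by side.

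1. **What the question can distinguish.** Under VI.A.2, criterion b, everyone enrolled receives prophylaxis regularly. VIII.A then asks the same people whether they do. Consider two subjects on a regular regimen, one who took the dose now due and one who missed it. Both can truthfully say yes. As worded, the question separates regular from irregular users, not covered from uncovered days.

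2. **What follows from a no.** At screening, a no means that criterion b is not met and the subject is ineligible. After enrolment, no section says to postpone, skip a procedure, wait for the dose or withdraw the subject. The stated triggers are different: discomfort during testing (VIII.A) and the subject's withdrawal of consent (VIII.B).

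3. **Whether another safeguard fills the gap.**
   - Exclusion e (VI.A.3) concerns major bleeding events, not dosing.
   - The low starting load, and the adjustment of manual and exercise therapy to the subject's current condition (VI.B.1.d), lower the risk but do not mention the dose.
   - The bleeding check in VI.B.1.g(ii) is the most specific bleeding safeguard in the protocol. It works from signs and so detects a bleed, not a missed dose.
   - Safety tracking (VI.B.2), therapist monitoring (VIII.B) and professional assistance during testing (VIII.A) are stated in general terms, without reference to dosing.
   - The halt rule (VIII.A) acts once discomfort is present.

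   None of these asks about the dose. The halt rule and the bleeding check act only after signs appear.

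4. **When the question is asked.** VIII.A places it before testing. The text does not say whether that includes the weekly sessions or whether the question is repeated. If testing means only the assessments, the weekly treatment sessions have no stated prophylaxis question. If it includes the sessions, the question is still about habit. The gap exists on either reading.

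5. **Effect on the analysis.** The sample size (9, raised to 10) and the pre/mid and pre/post Wilcoxon comparisons in VI.B.3 use nothing from VIII.A and are unaffected.

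**The case against.** The strongest reply is that the wording is being read too literally. Since everyone enrolled is already a regular user, a question put again before testing, in direct response to a bleeding risk, most usefully means whether the subject is keeping up the schedule. Physical therapists working with hemophilia patients may well ask about the last dose anyway, and a subject may volunteer a missed one. This stands in part. The intention may be right and practice may be better than the text, so the remedy is to write the intended question down. It does not supply an action for a no.

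A second reply is that no harm is shown. That stands in full as far as size is concerned. Whether one late dose matters for a session starting at 0.5 kg, or for a 6-minute walk, cannot be judged from these documents.

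Three stronger readings are tempting and are not supported:

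- A reader might infer that the study forms have no place to record prophylaxis. The daily-note list is introduced as what the note includes, the diary card is not shown, and the two may be one form. Only the protocol's description can be judged.
- A reader might infer from the three-occurrence withdrawal rule that testing must include the weekly sessions, because a third event at the third assessment would leave nothing to withdraw from. But each assessment contains at least two physical procedures (HJHS and 6MWT), so 2 × 2 = 4 have taken place by week 6 and a third event could fall then. VI.B.3 also uses pre-test, mid-test and post-test for the assessments. The rule does not settle the scope.
- A reader might infer that a physician must clear every late dose. The protocol has no such role: the listed investigators are physical therapists, and the Hemophilia Center appears only as a recruitment route.

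**Conclusion.** The point holds as a gap in a stated safety measure. Followed exactly, the VIII.A question repeats inclusion criterion b, does not establish whether the current scheduled dose was taken, and leads to no stated action if the answer after enrolment is no. No other described safeguard asks about the dose.

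No risk size is claimed. A reader might take this to mean that the study is unsafe or that subjects will be treated without cover, but the documents do not support that: they state several other safeguards and give no data from which a rate could be derived.

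The conclusion rests on reading the question as written and on the protocol's description of its records. It is a cheap improvement for patient safety with no bearing on the planned efficacy tests.

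**What to change.** In VIII.A, replace the question with: *Was the most recent scheduled prophylaxis dose taken, and when?* Ask it before each physical assessment (HJHS, 6MWT) and before each weekly session, and record the answer on the existing daily note or diary card.

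State the action. If the dose was missed or is overdue, the therapist does not increase load that day. The therapist then decides whether to go ahead with mobilization, stretching or physical assessment, or to postpone until the dose is taken, and records that decision and the actual date of any assessment that moves.

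The cost is a short amendment to VIII.A, one recorded answer per occasion, a little therapist time, and an occasional postponed session or assessment. Week 12 is the end of the intervention and no later study visit is scheduled, so a postponed week 12 assessment would need one extra visit. The planned comparisons stay the same, and recording actual dates lets any shift in timing be described.
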